### **Statement of Compliance**

This study will be conducted in accordance with the Code of Federal Regulations on the Protection of Human Subjects (45 CFR Part 46), 21 CFR Parts 50, 56, 312, and 812 as applicable, any other applicable US government research regulations, and institutional research policies and procedures. The International Conference on Harmonisation (“ICH”) Guideline for Good Clinical Practice (“GCP”) (sometimes referred to as “ICH-GCP” or “E6”) will be applied only to the extent that it is compatible with FDA and DHHS regulations. The Principal Investigator will assure that no deviation from, or changes to the protocol will take place without prior agreement from the sponsor and documented approval from the Institutional Review Board (IRB), except where necessary to eliminate an immediate hazard(s) to the trial participants. All personnel involved in the conduct of this study have completed Human Subjects Protection Training.

## Protocol Summary

Title	MELATONIN USE AFTER PRIMARY TOTAL JOINT ARTHROPLASTY: A RANDOMIZED, DOUBLE BLIND, PLACEBO-CONTROLLED TRIAL
Brief Summary	The purpose of this study is to determine the effect of melatonin supplementation on patient sleep quality, length of stay, and opioid consumption following primary, unilateral, elective total hip or knee arthroplasty.
Phase	N/A
Objectives	The primary objective is improved sleep quality postoperatively
Methodology	Single Center, randomized, double-blind, placebo-controlled clinical trial
Endpoint	The primary endpoint will be enrollment and completion of the study of 256 patients as pre-determined by statistical analysis.
Study Duration	Approximately 12 months (post IRB approvals)
Participant Duration	We estimate each patient will need to participate for roughly 60 days
Duration of IP administration	Patients will take the melatonin or placebo for 14 days
Population	Sample size will be 252 patients, both male and female patients will be included, all adult patients undergoing primary elective TKA or THA will be included. No vulnerable populations will be enrolled
Study Sites	Langone Orthopedic Hospital, New York, NY NYU Brooklyn Hospital, Brooklyn, NY
Number of participants	256 participants
Description of Study Agent/Procedure	Melatonin is an over-the-counter sleep aid
Reference Therapy	None
Key Procedures	Pre- and postoperative sleep survey, survey on quality of sleep, patient reported outcome questionnaires, narcotic consumption and pain daily for 14 days postoperatively
Statistical Analysis	Descriptive statistics will be used to report baseline characteristics and primary study objectives

## 1 Introduction, Background Information and Scientific Rationale

### 1.1 *Background Information and Relevant Literature*

Utilization of total hip and knee arthroplasty (THA and TKA, respectively) has increased over the last decade and is expected to continue to rise as the population of the United States ages. By 2030, over 2 million total joint arthroplasty (TJA) procedures are anticipated to be performed annually. With increasing numbers and to maintain excellent patient outcomes after total joint arthroplasty, it has become important to optimize every aspect of patient recovery. Sleep disturbance is a routinely encountered problem during the perioperative period in adults undergoing elective surgery. Sleep in postoperative patients is negatively influenced by exposure to anesthesia and the presence of postoperative pain. Reciprocally, poor sleep also portends poor coping and exacerbation of post-operative pain. Nighttime awakenings may be frequent, and require the use of additional pain medication to go back to sleep.

### 1.2 *Name and Description of the Investigational Agent*

#### 1.2.1 *Preclinical Data*

Melatonin or 5 methoxy-N-acetyltryptamine was discovered and isolated from bovine pineal gland in 1957. A naturally occurring hormone, melatonin is synthesized by pinealocytes from tryptophan and once synthesized released into the systemic circulation to reach several central and peripheral target tissues. Melatonin works through activation of ML1 and ML2 receptors in target cells through a G-protein coupled receptor – adenyl cyclase pathways. The molecule is important in regulation of human circadian rhythms such as the sleep-wake rhythm, neuroendocrine rhythms or body temperature cycles through its action on various target cells throughout the body. Consumption of melatonin, either orally or intravenously, induces fatigue, sleepiness and a diminution of sleep latency in humans. Given its physiologic effects, melatonin is an agent of great interest in perioperative patients experiencing sleep disturbance.

#### 1.2.2 *Clinical Data to Date*

Decreased levels of melatonin production have been observed in postoperative patients undergoing minor orthopedic procedures whether under general or regional anesthesia. Perioperative melatonin has been studied in other fields of surgery. Caumo et al have demonstrated preoperative administration of melatonin has been associated anxiolytic and analgesic effects in addition to increased potency of sleep/wake circadian rhythms in patients undergoing gynecologic procedures. Borazan et al demonstrated improved subjective sleep quality after prostate surgery after perioperative administration of melatonin. A systematic review of randomized trials with melatonin has demonstrated efficacy in reducing perioperative anxiety and some positive effects on perioperative pain.

### 1.3 *Rationale*

Sleep disruption following elective, primary total joint arthroplasty is very common. The cause is likely multifactorial, resulting from anxiety, anesthesia, the patient's recovery environment, and pain. Overall tiredness can lead to decreased energy, restlessness, less ambulation, and slow progress with physical therapy and recovery. Melatonin is an inexpensive, over the counter dietary supplement with an established safety profile that has been used to help create a more restful sleep cycle. There is no consensus as to the utility, dose, duration, or timing of melatonin administration in the period before and after elective hip and knee arthroplasty to improve sleep quality. This study design is supported by sleep disturbance usually occurs within the first 2 weeks of surgery due to a disrupted sleep wake cycle and pain. 5mg is a safe and effective starting dose for any sleep disturbance. Further, inconsistent methods of assessing patients' sleep and pain postoperatively has made the study of sleep quality difficult.

## **1.4 Potential Risks & Benefits**

### **1.4.1 Known Potential Risks**

Short term use of melatonin is safe, even in extreme doses with only mild adverse effects which can include dizziness, headache, nausea and sleepiness. Randomized clinical studies have indicated that even long-term exogenous melatonin only mild adverse effects such as dizziness and headaches comparable to placebo.

### **1.4.2 Known Potential Benefits**

In addition to its importance in regulation of human circadian rhythms such as the sleep-wake rhythm, neuroendocrine rhythms or body temperature cycles; perioperative melatonin is also known to reduce the incidence of delirium in older patients.

## **2 Objectives and Purpose**

### **2.1 Primary Objective**

The primary objective is the Epworth Sleep Score used to evaluate the impact of melatonin use on the quality of sleep, including total hours of sleep and nighttime awakenings in patients undergoing elective primary total hip and knee arthroplasty.

Secondary Objectives are to monitor and investigate hospital length of stay, and narcotic consumption patterns, scores in patients who take melatonin as a sleep aid for 14 days after surgery.

## **3 Study Design and Endpoints**

### **3.1 Description of Study Design**

This will be a single-center randomized double blind placebo control clinical trial. In the cohort of patients undergoing primary elective total hip and the cohort of patients undergoing primary elective knee arthroplasty, participants are recruited from those who are willing to consent and participate in the study, and will be randomly 1:1 divided into intervention group and placebo group.

Knee cohort:

- Intervention group will receive a 5mg Melatonin prescription for 14 days
- Control group will receive a placebo pill for 14 days

Hip cohort:

- Intervention group will receive a 5mg Melatonin prescription for 14 days
- Control group will receive a placebo pill for 14 days

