#### **4.5 Total Number of Participants and Sites**

252 patients will be recruited at NYU Langone Orthopedic Hospital and NYU Brooklyn Hospital.

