## **8.4 Description of Statistical Methods**

### **8.4.1 Analysis of the Primary Efficacy Endpoint**

The primary outcome, the ESS score measured at days 1-14 postoperatively for each group, will be summarized using means, standard deviation, median and inter quartile ranges. In the main analysis, the ESS score of the control and intervention group in either THA or TKA cohort will be compared using repeated measures ANOVA. Significant tests will be two-sided at significant level at 0.05.

The normality assumption of the primary efficacy outcome will be checked and strategies to transform the outcome variable will be considered. As a sensitivity analysis, the ANOVA will be replaced with the Wilcoxon rank sum test to ensure the robustness of the results.

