## **8.5 Measures to Minimize Bias**

### **8.5.1 Enrollment/Randomization/Masking Procedures**

Research assistants not involved in the study protocol will be responsible for maintaining the patient database and randomization algorithm. Treatment will begin on postoperative day zero. The control groups will receive 14 placebo pills. The treatment group will receive 14 pills of 5mg melatonin. Patients will begin taking a daily pill for 14 days postoperatively. They will continue to receive their selected treatment during their inpatient hospital stay.

Block randomization will be done through RedCap to ensure equal distribution of intervention vs control subjects. The block size will be undisclosed. There will be no stratification based on age, gender, or surgery type.

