## **12 Data Handling and Record Keeping**

### ***12.1 Data Collection and Management Responsibilities***

Data collection is the responsibility of the clinical trial staff at the site under the supervision of the site PI. The investigator is responsible for ensuring the accuracy, completeness, legibility, and timeliness of the data reported.

All source documents should be completed in a neat, legible manner to ensure accurate interpretation of data. Black ink is required to ensure clarity of reproduced copies. When making changes or corrections, cross out the original entry with a single line, and initial and date the change. DO NOT ERASE, OVERWRITE, OR USE CORRECTION FLUID OR TAPE ON THE ORIGINAL.

Copies of the electronic CRF (eCRF) will be provided for use as source documents and maintained for recording data for each participant enrolled in the study. Data reported in the eCRF derived from source documents should be consistent with the source documents or the discrepancies should be explained and captured in a progress note and maintained in the participant's official electronic study record.

Clinical data (including AEs, concomitant medications, and expected adverse reactions data) and clinical laboratory data will be entered into a RedCap database, a encrypted, HIPAA-compliant data capture system managed by MCIT. The data system includes password protection and internal quality checks, such as automatic range checks, to identify data that appear inconsistent, incomplete, or inaccurate. Clinical data will be entered directly from the source documents. Each site will have access to its identifiable data. Only de-identified data will be passed between institutions.

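### The trial is labelled single-center but recruits at two hospitals, and hospital appears in neither the described randomization nor the primary analysis; this costs a little precision and does not cause bias

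*Combined protocol and SAP*

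**What the plan says.** **Design label.** Section 3.1: "This will be a single-center randomized double blind placebo control clinical trial". The Methodology row of the Protocol Summary agrees: "Single Center, randomized, double-blind, placebo-controlled clinical trial".

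**Sites.** The Study Sites row of the same summary lists two: "Langone Orthopedic Hospital, New York, NY NYU Brooklyn Hospital, Brooklyn, NY". Section 4.5 repeats them: "252 patients will be recruited at NYU Langone Orthopedic Hospital and NYU Brooklyn Hospital". No split between the hospitals is given. Section 12.1 is also worded for more than one site ("Each site will have access to its identifiable data"), though that may be template text.

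**Randomization.** Section 8.5.1: "Block randomization will be done through RedCap to ensure equal distribution of intervention vs control subjects". It continues: "There will be no stratification based on age, gender, or surgery type". Hospital is neither included nor ruled out.

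**Analysis.** Section 8.4.1 states that "the ESS score of the control and intervention group in either THA or TKA cohort will be compared using repeated measures ANOVA", with a Wilcoxon rank sum test as sensitivity analysis. Neither has a hospital term. Section 8.3 keeps the hip and knee cohorts separate throughout. Section 8.4.2 lists secondary endpoints but states no model for them. Hospital is not among the baseline characteristics named in section 8.4.5, nor is it named as a subgroup in section 8.4.6.

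**The concern.** The label and the site list do not agree. One institution with two campuses would reconcile them, but no section says so, and the label would carry into reports of the trial.

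The statistical side follows from the second hospital. Some outcomes arise partly on the ward: section 6.1.1 takes opioid use from in-patient records, length of stay is a secondary objective in section 2.1, and section 1.3 names the recovery environment as a likely contributor to poor sleep. If the hospitals differ on an outcome, that difference is part of the outcome variance. An unstratified list does not hold the arms to the same hospital mix within a cohort, and the planned ANOVA has nothing to take the difference out.

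Two things are at stake. One is some precision. The other is what happens if an imbalance is seen in the final data: a hospital term added then would be a choice made after seeing the result. Since hospital is not in the planned baseline table, an imbalance might also go unreported.

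**Working it through.** **Inputs from the documents (section 8.2):** difference 2.65 ESS points, SD 5.3, two-sided alpha 0.05, power 80%, 64 per arm in each cohort.

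**Assumptions (not in the documents):** share p of patients at the smaller hospital, 20-50%; difference d between hospitals in mean ESS, 1 to 2.65 points.

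**1. The plan's own figure.** The standardized difference is 2.65/5.3 = 0.5. A two-sample t-test needs 63.8 per arm, rounded up to 64, and power at 64 is 0.801. The stated sample size is reproduced and does not depend on this point.

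**2. Chance imbalance within a cohort.** SD of the arm difference in hospital share = sqrt(2p(1−p)/64).

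| p | SD (points) | 95% range, ±1.96 SD (points) |
|---|---|---|
| 0.2 | 7.1 | ±13.9 |
| 0.3 | 8.1 | ±15.9 |
| 0.5 | 8.8 | ±17.3 |

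**3. Shift in the estimated arm difference.** Shift = imbalance × d.

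- d = 1: the 95% limit is 0.14 to 0.17 ESS points.
- d = 2.65: the 95% limit is 0.37 to 0.46 ESS points.

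The comparator is the standard error of the arm difference, 5.3 × sqrt(2/64) = 0.94. The largest of these shifts is 0.46/0.94, about half a standard error.

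**4. Validity of the unadjusted test.** Simulation with 40,000 trials per setting (p = 0.3 and 0.5 with d = 2.65; p = 0.5 with d = 5.3) gave a type I error of 0.049 to 0.051. With a true difference of 2.65, the mean estimates were 2.65 to 2.66.

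**5. Power with a hospital term.** Residual SD = sqrt(5.3² − p(1−p)d²), with 64 per arm and a t-test on 125 degrees of freedom (128 − 3).

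| p | d = 1: residual SD, power | d = 2.65: residual SD, power |
|---|---|---|
| 0.2 | 5.285, 0.804 | 5.193, 0.817 |
| 0.3 | 5.280, 0.804 | 5.159, 0.822 |
| 0.5 | 5.276, 0.805 | 5.132, 0.826 |

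The starting value is 0.801. For a 1-point hospital difference the gain is close to nothing. For a difference as large as the MCID it is 1.6 to 2.5 percentage points.

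**6. What stratification would achieve.** Simulated with blocks of 4 (assumed, since the block size is undisclosed), 128 per cohort and p = 0.3. The 95% range of hospital imbalance within a cohort was:

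- no stratification: about ±16 points;
- hospital only: about ±11 points;
- hospital and surgery type together: about ±2 points.

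Stratifying by hospital alone leaves about 70% of the imbalance (11/16), because each block mixes hips and knees while the analysis separates them.

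**The case against.** The strongest reply is that nothing is wrong with the planned comparison. Under 1:1 randomization an unstratified, unadjusted analysis is valid, and hospital imbalance is one more source of random error already in the standard error. That stands, and step 4 confirms it. A reader might infer from the missing hospital term that the arm comparison is biased or its type I error inflated; neither follows.

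A reader might also reach a much larger effect by taking the 95% limit at p = 0.3 (0.159) and a hospital difference of 0.5 to 1 SD. The shift is then 0.08 to 0.16 SD, or 16-32% of the 0.5 SD design difference. The documents do not support that as a headline. On the ESS, 1 SD is 5.3 points, twice the MCID, and no section suggests such a gap between hospitals in daytime sleepiness. The calculation also pairs an extreme imbalance with an assumed large difference. Against the standard error of sqrt(2/64) = 0.177 SD, even that shift is about 0.45 to 0.9 standard errors. The outcomes most likely to depend on the ward are opioid use and length of stay, for which the plan states no design difference to scale against.

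Two further replies stand in part. Section 8.5.1 is silent on hospital, so separate lists per hospital are possible, though none is described. Single-center may mean one institution, and the study product is held in one department's office, but the text never defines the term.

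**Conclusion.** The point holds as a minor one. The design label conflicts with the two named hospitals, and hospital is absent from the described randomization and from the primary analysis. The consequence is avoidable noise and an unplanned decision if an imbalance appears. The stated 64 per arm is unaffected and no change in sample size follows.

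The size rests on two assumptions that the documents cannot settle. At 20-50% of patients in the smaller hospital, imbalance within a cohort has a 95% range of about ±14 to ±17 points. At a hospital difference of 1 to 2.65 ESS points, adjustment takes power from about 0.80 to 0.80-0.83. If the hospitals do not differ on the ESS, there is nothing to gain on the primary endpoint beyond having the rule fixed in advance.

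**What to change.** 1. In the Protocol Summary and section 3.1, replace the single-center label with two hospitals under one institution.
2. In section 8.4.1, pre-specify hospital as a fixed effect in the repeated measures model for each cohort. The Wilcoxon test takes no such term and can stay as the unadjusted sensitivity analysis.
3. Section 8.4.2 has no model to amend. State one for each secondary endpoint, including length of stay (an objective in section 2.1 that 8.4.2 does not list), and include hospital in it.
4. Add hospital by arm to the baseline table in section 8.4.5.
5. If enrolment has not started, stratify the REDCap blocks by hospital and surgery type together, and revise the sentence in section 8.5.1 that rules out surgery type. Hospital alone would not be enough, as step 6 of the working shows. If enrolment has started, leave the list as it is and rely on the model term.

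The cost is one degree of freedom per model, one REDCap setting and a few lines of text. Hospital is known for every patient, so no new data are needed.

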### **3.2 Study Endpoints**

#### **3.2.1 Primary Study Endpoints**

The primary endpoint will be the Epworth Sleep Score for patients indicating the impact of melatonin on quality of sleep, including total hours of sleep and nighttime awakening. The ESS will be evaluated post-operatively from days 1-14.

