### **6.2 Study Schedule**

Procedure	Screening/Visit 1 (SOC visit within - 3 months of surgery)	Surgery	Visit 2 (SOC visit within +2 months of surgery)
-----------	---	---------	--

Screening	X (Research only)		
Consent	X (Research Only)		
Medical History	X (SOC)		
Surgical History	X (SOC)		
Demographics	X (SOC)		
Distribute medication		X (Research Only)	
Collect pill bottle			X (Research Only)
Collect Adverse Events			X (Research Only)
Collect Questionnaires and peri-operative data (in-patient opioid consumption, Epworth and Stanford sleepiness scale, VAS Pain Scale)		X (Research Only)	X (Research Only)
Collect Sleep Diary			X (Research Only)

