### 6.2.2 Enrollment/Baseline

#### Enrollment/Baseline Visit (Visit 1)

- Review medical history to determine eligibility based on inclusion/exclusion criteria.
- Obtain informed consent of potential participant verified by signature on study informed consent form.
- Obtain and record vital signs, results of examinations, demographic information, medical history, medication history, alcohol and tobacco use history, and other assessments from the medical records.
- Record PROMIS – Sleep Disturbance

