#### **Visit 2 (standard of care post-operatively visit within 2 months of surgery)**

- Observe patient's recovery from TJA surgery as per standard of care
- Record participant's adherence to treatment program.
- Record patient standard sleepiness scale, PROMIS – Sleep Disturbance, VAS pain scores, collect sleep diary and opioid consumption.

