### **8.4.2 Analysis of the Secondary Efficacy Endpoints**

The secondary endpoints include number of total hours of sleep, number of nighttime awakenings, and narcotic consumption.

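### The primary conclusion is worded as sleep quality, but the Epworth score is a sleepiness scale, and the sleep-disturbance questionnaire collected before and after surgery is assigned to no endpoint or analysis

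*Combined protocol and SAP*

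**What the plan says.** The Protocol Summary gives better postoperative sleep quality as the primary objective. Section 2.1 names the Epworth score as the means of judging it and counts hours of sleep and awakenings as part of sleep quality. Section 3.2.1 repeats this, describing the Epworth score as "indicating the impact of melatonin on quality of sleep, including total hours of sleep and nighttime awakening".

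Elsewhere the same document describes the instrument and the drug differently:

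- The Section 6.2 schedule lists the "Epworth and Stanford sleepiness scale". Reference 21, which supplies the MCID, also has the Epworth instrument in its title as a sleepiness scale.
- Section 1.2.1 says melatonin "induces fatigue, sleepiness and a diminution of sleep latency in humans". Section 1.4.1 gives its mild adverse effects as "dizziness, headache, nausea and sleepiness".
- Section 8.4.2 states: "The secondary endpoints include number of total hours of sleep, number of nighttime awakenings, and narcotic consumption". Section 8.1 gives hours of sleep a separate secondary hypothesis, measured daily on days 1-14.

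A sleep-disturbance questionnaire is also collected. The Visit 1 text says "Record PROMIS – Sleep Disturbance". The Visit 2 text says "Record patient standard sleepiness scale, PROMIS – Sleep Disturbance, VAS pain scores, collect sleep diary and opioid consumption".

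**The concern.** A score of sleepiness and a statement about sleep quality are different things. With this drug the gap matters, because the protocol itself says melatonin produces sleepiness. The ESS could therefore move through the drug's own action as well as through better or worse nights, and the two need not point the same way. A trial run and reported as written would turn a sleepiness result, positive or null, into a statement about sleep quality, hours and awakenings.

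Meanwhile the questionnaire whose name matches the stated objective is collected before and after surgery with no role in the analysis. If it stays unassigned, any later use of it will look chosen after the results were seen.

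**Working it through.** This is mainly a question of what is measured, so the sections are compared first. The arithmetic covers only what the sample size supports.

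**1. What the ESS is said to show, and what is tested**

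| Place | Content |
|---|---|
| Protocol Summary | Primary objective: sleep quality |
| 2.1, 3.2.1 | ESS stands for sleep quality, with hours and awakenings included |
| 6.2, reference 21 | The Epworth instrument is a sleepiness scale |
| 8.1 | Primary null hypothesis: mean ESS, days 1-14 |
| 8.2 | Sample size: ESS only |
| 8.4.1 | Primary test: ESS only |
| 8.1, 8.4.2 | Hours (both sections) and awakenings (8.4.2): secondary |

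The statistical sections agree with one another: the ESS is primary, and hours and awakenings are secondary. Only the Summary, 2.1 and 3.2.1 attach a wider meaning to the score. Hours have their own daily hypothesis and a daily sleep diary is kept (6.1.1), so the plan itself does not rely on the ESS to measure them.

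**2. Where PROMIS – Sleep Disturbance appears**

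It is in the text for Visit 1 and Visit 2. It is absent from the 6.2 schedule table and from Sections 2.1, 3.2.1, 8.1, 8.2, 8.4.1 and 8.4.2. Section 8.1 ends with an unfilled line saying that more secondary endpoints will be listed; PROMIS is not named there. The Summary and 6.1.1 also mention a survey on quality of sleep without identifying the instrument or assigning it to an endpoint.

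On timing, the schedule allows Visit 2 up to 2 months after surgery, whereas treatment and the primary window cover 14 days. Section 5.1.8 mentions a 2-week postoperative visit, but nothing places PROMIS at it.

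**3. The plan's own sample size**

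Inputs from 8.2: difference 2.65, SD 5.3, two-sided alpha 0.05, power 80%.

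- Standardized difference: 2.65 / 5.3 = 0.50.
- Normal approximation: n per arm = 2 × (1.960 + 0.842)² / 0.50² = 62.8, rounded up to 63.
- Two-sample t-test (equivalently a two-group ANOVA): 63.77, rounded up to 64 per arm. That is 128 per cohort and 256 in all.

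The stated 64 is reproduced. It covers a difference in the ESS and nothing else.

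**4. What 64 per arm might give for PROMIS (illustration only)**

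The documents give no SD, MCID or expected effect for PROMIS, so both the effect d (in SD units) and the baseline-outcome correlation r are assumptions. Adjusting for the Visit 1 score by ANCOVA makes the effective standardized difference d / √(1 − r²). For example, d = 0.4 and r = 0.6 give 0.4 / √0.64 = 0.50, and hence 80% power. Two-sided t-test power at 64 per arm:

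| Assumed d | r = 0.3 | r = 0.6 |
|---|---|---|
| 0.3 | 42% | 56% |
| 0.4 | 65% | 80% |
| 0.5 | 84% | 94% |

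The schedule lets Visit 1 fall up to 3 months before surgery, so even r = 0.3 is not assured.

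**The case against.** The strongest reply is that the operative text already settles the matter. The hypothesis, the sample size and the primary test all use the ESS alone, and 3.2.1 says the score indicates an effect on hours and awakenings, not that these are co-primary. That stands. A reader might infer, from seeing hours and awakenings in both the primary statement and the secondary list, that primary success could be claimed from hours if the ESS fails. Sections 8.1, 8.2 and 8.4.1 do not support that reading.

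A second reply is that drug-induced sleepiness need not reach the ESS. Section 5.1.5 has the pill taken within an hour of bedtime, and 1.2.1 mentions sleepiness alongside shorter sleep latency, which is an intended effect. No section gives the size of any carry-over. This also stands: a reader might infer that the ESS will worsen while sleep improves, but the documents show only that the two can differ.

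A third reply is that the secondary list in 8.1 is openly unfinished, so PROMIS may have been intended. It may have been, but an unfilled placeholder does not pre-specify an endpoint, a time point or a method.

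None of these replies makes a sleepiness score a measure of sleep quality.

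**Conclusion.** The concern holds as a mismatch between instrument and conclusion, together with a relevant measure left unassigned. It should be corrected, but it does not undermine the primary test: the ESS can legitimately stay primary, and the sample size reproduces.

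Its size cannot be stated as a bias in ESS points, because the documents give no figure for a melatonin-induced shift in sleepiness. Nor do they support two convenient inferences about PROMIS:

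- **That it comes free.** As scheduled, its postoperative value may be taken up to 2 months after surgery, so a measurement near the end of treatment needs a set time.
- **That it is well powered.** The 84-94% range holds only at an assumed 0.5 SD. At 0.3 to 0.4 SD, with the same assumed correlations, the range is 42-80%.

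**What to change.** 1. Keep the ESS as the primary endpoint and leave the sample size unchanged.
2. In the Protocol Summary, 2.1 and 3.2.1, state the primary objective and endpoint as sleepiness and remove the wording that makes the score stand for sleep quality, hours and awakenings. All three places need the edit; otherwise the Summary will contradict the endpoint section. Report the ESS result as sleepiness.
3. List hours of sleep and awakenings as secondary only, consistent with 8.1 and 8.4.2.
4. Name PROMIS – Sleep Disturbance as a secondary endpoint in 8.1 and 8.4.2, compared between arms by ANCOVA on the Visit 1 score, separately in the THA and TKA cohorts. Because 11.3.2 allows consent on the day of surgery and enrollment afterwards, say when the baseline score is taken for those patients.
5. Add PROMIS to the 6.2 schedule table, and set its postoperative completion at day 14 with the diary or at the 2-week visit mentioned in 5.1.8.
6. Base any statement about sleep quality on PROMIS and the diary, and claim no power for PROMIS.

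The cost is a narrower claim from the primary test, one timed questionnaire and one additional analysis per cohort. The changes should be made before unblinding.
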